5.1.4.2 Gastric Residuals – Full-calorie Feeding Group

Gastric residuals in the full-calorie feeding group will be checked every 6 to 12 hours according to the full-calorie feeding protocol (see Appendix D). If GRV remains less than or equal to 400 cc, GRV will be replaced tube feeds will be advanced or maintained if already at full-calorie rate. After the first episode of GRV greater than 400 cc, 400 cc of the GRV will be replaced, the feeding rate will be maintained at the current rate and residuals will be rechecked in 2 hours. After the second episode of GRV greater than 400 cc, tube feeds will be held. 400 cc of the GRV will be replaced and rechecked every 2 hours. Tube feeds will continue to be held until gastric residuals are less than 400 cc. Once GRV is less than or equal to 400 cc, GRV will be replaced and tube feeds will be restarted at 25 cc / hr less than the previous rate.

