2.4 Secondary Hypotheses

- The timing of advancing enteral feeds to full feeding rates will alter plasma IL-6 and IL-8 levels in patients with ALI or ARDS compared to early, full-calorie enteral feeding.
- Initial trophic feeding followed by full-calorie enteral feeding will decrease the incidence of gastrointestinal intolerances (vomiting, aspiration, regurgitation, diarrhea, elevated gastric residual volumes, and abdominal distention and cramping) compared to early, full-calorie enteral feeding.
- Initial trophic feeding followed by full-calorie enteral feeding will decrease the incidence
 of ventilator-associated pneumonia in patients with ALI or ARDS compared to early,
 full-calorie enteral feeding.
- Initial trophic feeding followed by full-calorie enteral feeding will decrease the incidence
 of developing bacteremia in patients with ALI or ARDS compared to early, full-calorie
 enteral feeding.

3 End Points

Analysis of primary and all secondary endpoints will be conducted on an intention to treat basis. A secondary analysis will be performed looking at patients who achieved greater than 70% of full-calorie feeds for the initial 6 days.

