3.3 Other Endpoints

Many of these proposed outcomes are not meant to definitively establish the underlying mechanisms, but instead will explore biochemical endpoints to provide additional support or generate other hypotheses of how the interventions may result in different clinical outcomes.

- 1. Increase of PaO₂ / FiO₂ ratio on study days 1-7
- 2. Improvement in Lung Injury Score on study days 1-7
- 3. Number of gastrointestinal intolerances (aspiration, vomiting, regurgitation, diarrhea, elevated gastric residual volumes, abdominal distention and cramping) on study days 1-7
- 4. Level of systemic inflammation, as measured by plasma IL-6 and IL-8 levels.

5.

- 6. Measure of oxidative stress on days 3, 6 and 12 compared to baseline as measured by urinary levels of F₂-isoprostane metabolites
- 7. Incidence of bacteremia.
- 8. Incidence of Clostridium dificile induced diarrhea.
- 9. Incidence of ventilator-associated pneumonia
- 10. Serum levels of markers of nutrition, including albumin and total protein levels between baseline and days 6 and 12.

Clostridium dificile diarrhea will be diagnosed by one or more daily stool specimen positive for cytotoxin assay or enzyme immunoassay. Patients with more than 3 liquid stools totaling more than an estimated 500 ml of stool per day, or those with systemic inflammatory response

syndrome unexplained by other infection, may have up to three daily stool samples sent for *C. difficile* investigation (either cytotoxin assay or enzyme immunoassay).

Bacteremia will only be considered if it develops greater than 24 hours after the initiation of study procedures and is documented with a positive blood culture. The primary medical team, using clinical judgment, will determine when blood cultures are sent. Coagulase negative (or thermo nuclease negative) *Staphylococci* or *Corynebacterium* bacteremia require the isolation of these organisms from at least two blood cultures drawn within 24 hours of each other containing the same organism in order to be deemed significant.

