5.1.3.1 Trophic Enteral Feeding Treatment Group (Trophic Feeding Group)

All patients randomized to trophic enteral feedings will have enteral feeds started at 20 kcal / hr and continued at this rate for 144 hours (see Trophic Feeding Protocol, Appendix C) provided gastric residuals remain at an acceptable level (see Gastric Residuals, section 5.1.4) and provided the patient remains on the ventilator. Thus, patients in the trophic feeding arm will receive 480 kcal, which is approximately 25% of total caloric goals each day. This caloric delivery lies within the range of data from published studies in animals and neonatal humans (Burrin, 2000; McClure, 2000; Ohta, 2003; Omura, 2000; Owens, 2002; Tyson, 2005). After 144 hours of trophic enteral feeds, the feeding rate will be advanced to full-calorie rates using the same protocol as for the full-calorie feeding treatment group (see section 5.1.3.2 and Appendix D) provided the patient remains on the ventilator.

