5.1.4.1 Gastric Residuals -Trophic Feeding Group

GRVs will be checked every 12 hours while patients are receiving trophic feeding rates. If GRV remains less than or equal to 400 cc, GRV will be replaced and tube feeds will continue at 20 kcal / hr (see Appendix C). If GRV exceeds 400 cc, 400 cc of the residual volume will be replaced, tube feeds will continue at 20 kcal / hr and GRV will be rechecked in 2 hours. If GRV remains greater than 400 cc, tube feeds will be held. GRV will be replaced (up to 400 cc) and gastric residual rechecked every 2 hours. Tube feeds will continue to be held until residual volume is less than or equal to 400 cc. Once residual volume is less than or equal to 400 cc, trophic tube feeds will be restarted at a rate of 20 kcal / hr.

When the trophic feeding group is advanced to full-calorie enteral feeds (after 144 hours of trophic feeds), GRVs will be checked according to the full-calorie feeding protocol (see section 5.1.4.2 and Appendix D).

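### Elevated gastric residuals count toward the intolerance endpoint but get more scheduled checks in the full-calorie arm, which tilts that component toward the trophic hypothesis

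*Protocol*

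**What the plan says.** Protocol 3.3, item 3, lists this endpoint: "Number of gastrointestinal intolerances (aspiration, vomiting, regurgitation, diarrhea, elevated gastric residual volumes, abdominal distention and cramping) on study days 1-7". Section 2.4 attaches a direction to the same set of events, again naming elevated residuals: trophic-first feeding "will decrease the incidence of gastrointestinal intolerances".

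The routine check intervals differ by arm. In the trophic arm (5.1.4.1), "GRVs will be checked every 12 hours while patients are receiving trophic feeding rates". In the full-calorie arm (5.1.4.2), "Gastric residuals in the full-calorie feeding group will be checked every 6 to 12 hours according to the full-calorie feeding protocol".

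The response to a first high value is the same in both. In the trophic arm "tube feeds will continue at 20 kcal / hr and GRV will be rechecked in 2 hours"; in the full-calorie arm "the feeding rate will be maintained at the current rate and residuals will be rechecked in 2 hours".

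The trophic rate is "continued at this rate for 144 hours" (5.1.3.1). After that the trophic arm is advanced, and its "GRVs will be checked according to the full-calorie feeding protocol" (5.1.4.1). Section 6.3, item 15, records intolerances as a daily number and type with a 24-hour look-back.

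**The concern.** A high residual is recorded only if someone measures it, so the number recorded depends on how often it is sought as well as on how often it occurs. Here the measuring schedule is tied to the randomized arm. With identical residuals in both arms, staff who follow the protocol exactly would still have more opportunities to record an elevated GRV under full-calorie feeding during the trophic phase. The comparison is also unblinded.

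The direction matters, because extra detections in the full-calorie arm look like support for the hypothesis that trophic feeding causes fewer intolerances. A reader of the pooled count could not tell how much of a difference came from extra looks.

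This needs settling at data capture. If the form holds only the daily number and type, later analysis can separate GRV from the other intolerances. It cannot separate readings at the common 12-hourly times from intermediate checks and rechecks.

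**Working it through.** The protocol gives no figure of its own for this point, so there is none to reproduce.

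**Inputs from the protocol**
- Trophic phase: 144 h (5.1.3.1).
- Check interval: 12 h trophic (5.1.4.1); 6 to 12 h full-calorie (5.1.4.2).
- Rate steps in the full-calorie arm: every 6 h until goal (5.1.3.2).
- Time to goal in the phase II data: 11 h on average, 75% of patients within 15 h (1.4).

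**Step 1: scheduled checks over 144 h**

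Trophic arm: 144/12 = 12.

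Full-calorie arm, with 6-hourly checks for the first *a* hours and 12-hourly afterwards: n(a) = a/6 + (144 − a)/12.

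| a (hours at 6-hourly) | n(a) | ratio to 12 |
|---|---|---|
| 0 | 12 | 1.00 |
| 11 | 12.92 | 1.08 |
| 15 | 13.25 | 1.10 |
| 24 | 14 | 1.17 |
| 72 | 18 | 1.50 |
| 144 | 24 | 2.00 |

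The value of *a* is an assumption, since Appendix D governs it and its chart could not be read. If the 6-hourly interval goes with rate advancement, *a* is about 11 to 24 h. The 24 h case corresponds, for example, to a predicted body weight of 80 kg at 35 kcal/kg and an assumed 1 kcal/cc: 80 × 35/24 = 116.7 cc/h, which takes four 6-hour steps from 25 cc/h.

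**Step 2: from checks to detected episodes**

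Suppose the same process of high-residual episodes in both arms, with exponential length of mean D hours (assumed). An episode is detected if a scheduled check falls within it. With checks every T hours, P(detected) = (D/T)(1 − exp(−T/D)).

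| D (h) | P, T = 6 | P, T = 12 | ratio, 6-hourly throughout | ratio, 6-hourly for first 18 h only |
|---|---|---|---|---|
| 2 | 0.317 | 0.166 | 1.91 | 1.11 |
| 6 | 0.632 | 0.432 | 1.46 | 1.06 |
| 12 | 0.787 | 0.632 | 1.24 | 1.03 |
| 24 | 0.885 | 0.787 | 1.12 | 1.02 |

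The last column is (18·P₆ + 126·P₁₂)/(144·P₁₂). The longer a high residual lasts, the less the extra checks add, because the next 12-hourly check would have found it.

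**Step 3: after the fix**

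On the 12-hourly grid common to both arms, each has 144/12 = 12 scoring opportunities, a ratio of 1.0.

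**The case against.** Several counter-arguments have force.

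*The twofold figure is a ceiling.* It needs 6-hourly checks for all 144 hours, which no readable text says. The only visible 6-hour step is rate advancement, which in the phase II data was usually short. This stands. Stepping back up after a hold could lengthen the 6-hourly period, but that too is inference.

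*Extra checks are not extra episodes in proportion.* This stands, as step 2 shows. A reader might apply a fixed probability per independent check and announce a false excess of 17% to 100%. The documents give no such probability. Independence ignores persistence, and the 17% floor assumes 24 h at 6-hourly when the phase II times suggest less for most patients.

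*Rechecks are the same in both arms.* True. The 2-hour rule is not itself an arm difference, and no text says that each recheck counts as a separate intolerance. Counting rules may lie in an analysis plan or form instructions not shown, and their absence here is no fault.

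*The trophic arm later takes the full-calorie schedule.* For patients still ventilated at 144 h, a 6-hourly spell during their own advancement could offset some of the excess over days 1-7. It does nothing for patients off the ventilator sooner.

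*This is one component of an item under Other Endpoints.* True, and it limits the weight of the point. It does not remove it, because the same component is named in the directional hypothesis.

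A reader might also infer that the day 1-7 window is wrong because it runs past the trophic phase. The documents do not support that. The strategy randomized, and named in 2.4, is trophic feeding first and full-calorie feeding afterwards, so the days after advancement belong to the comparison.

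**Conclusion.** The point holds for the GRV component. The protocol fixes unequal scheduled ascertainment on an event that it counts and for which it predicts a direction. Over the trophic phase the full-calorie arm has 12 to 24 scheduled checks against 12. If 6-hourly checks end at goal rate, the excess in checks is about 8-17%. The excess in detected episodes is then smaller still: about 2-11% if 6-hourly checks last 18 h and mean episodes last 2 to 24 h. The exact size cannot be fixed without Appendix D and without knowing how long high residuals last.

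The bias in the trophic phase favours the trophic hypothesis. It does not act directly on aspiration, vomiting, regurgitation, diarrhea or distention/cramping. The primary endpoint, its power and the stopping boundaries are unaffected. It would go too far to say that any observed reduction in intolerances would be produced by the check schedule.

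**What to change.** Leave the bedside checks in 5.1.4.1 and 5.1.4.2 as they are and change only the scoring, in section 3.3:

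1. Score elevated GRV as yes/no at the 12-hourly checks common to both arms. Do not count intermediate 6-hourly checks or 2-hour rechecks.
2. Report elevated GRV separately from the clinical intolerances (aspiration, vomiting, regurgitation, diarrhea, distention/cramping).

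The day 1-7 window may stay. A count limited to the first 144 hours is at most an optional supplementary summary. Do not divide by days on study feeding: under 5.1.8 that time ends with death, discharge or extubation, so it is a post-randomization quantity.

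The cost is one case report form field, a sentence or two in 3.3, and some full-calorie GRV readings left out of the comparison. At least 272 patients were already enrolled (4.1), and those enrolled before the change may have only the daily number and type. For them, report the GRV component separately and state the unequal check schedule beside it.

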5.1.3.2 Full-calorie Enteral Feeding Treatment Group (Full-calorie Feeding Group)

The full-calorie feeding group will have enteral feeds initiated at 25 cc / hr. If gastric residuals remain at an acceptable level (see Gastric Residuals, section 5.1.4), the feeding rate will be increased by 25 cc / hr every 6 hours until goal rate (as determined by the dietary evaluation if available) is achieved (see Full-calorie Feeding Protocol, Appendix D). This pattern of advancement is similar to advancement rates used in other feeding trials (Adam, 1997; Rice, 2005).

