5.1.7.1 Abdominal Distention/Cramping

Abdominal distention or cramping is defined as the presence of a tense abdomen, rigidity, guarding or rebound on exam.

For patients receiving trophic feeds, enteral feeds will be held for abdominal cramping or distention. Enteral feeding will be resumed at 20 kcal / hr in this group after 6 hours or improvement of distention or cramping, whichever occurs first.

When abdominal distention or cramping occurs in patients randomized to full-calorie feeding rates, the enteral feeding rate will be decreased by 25 cc / hr to a minimum rate of 10 cc / hr. The abdomen will be re-evaluated 6 hours later. If the distention or cramping is improved, the enteral feeds will be advanced to full-calorie rates per the full-calorie feeding protocol as long as GRVs are acceptable (see Appendix D). If, after 6 hours, the abdominal distention or cramping is not improved, then enteral feeding will be held and resumed at the 25 cc less/ hr rate after 6 additional hours or improvement of the abdominal distention or cramping, which ever occurs first

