5.1.7.4 Vomiting

Vomiting is defined as the forceful expulsion of gastric contents from the oropharynx or nasopharynx.

When vomiting occurs, enteral feeds will be held for 6 hours. Six hours after the last episode of vomiting, enteral feeds will be restarted at 25 cc / hr less than the previous rate (minimum of 10 cc / hr) for the full-calorie feeding group, and 20 kcal / hr for the trophic feeding group.

The use of pro-kinetic agents and/or advancing the distal location of the feeding tube to a post-pyloric position should be considered in patients who experience vomiting.

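### The full-calorie restart rule after a gastric-residual hold (5.1.4.2) states no minimum, gives 0 cc/hr at the starting rate, and does not match the other 25 cc/hr reduction rules for the same arm

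*Protocol*

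**What the plan says.** Protocol section 5.1.3.2 sets the start and the step for this arm: "The full-calorie feeding group will have enteral feeds initiated at 25 cc / hr", and, if residuals are acceptable, "the feeding rate will be increased by 25 cc / hr every 6 hours until goal rate" is reached.

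Section 5.1.4.2 covers high residuals. A first GRV above 400 cc leaves the rate unchanged, with a recheck after 2 hours. Then: "After the second episode of GRV greater than 400 cc, tube feeds will be held". When the residual has fallen back to 400 cc or below, the instruction is that "tube feeds will be restarted at 25 cc / hr less than the previous rate". No minimum follows.

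Four other rules for the same arm make the same 25 cc/hr reduction and do state a minimum:

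- Distention or cramping (5.1.7.1): "the enteral feeding rate will be decreased by 25 cc / hr to a minimum rate of 10 cc / hr".
- Aspiration (5.1.7.2): the same reduction and minimum, for either tube position.
- Regurgitation with GRV above 400 cc (5.1.7.3): a 6-hour hold, then the same reduction and minimum.
- Vomiting (5.1.7.4): "enteral feeds will be restarted at 25 cc / hr less than the previous rate (minimum of 10 cc / hr").

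The diarrhea and constipation rules (5.1.7.5 and 5.1.7.6) set no numerical reduction.

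In the trophic arm, the matching residual rule (5.1.4.1) says "trophic tube feeds will be restarted at a rate of 20 kcal / hr". The same section sends trophic patients to 5.1.4.2 and Appendix D once they advance after 144 hours. Sections 5.1.4 and 5.1.4.2 both refer to Appendix D for the full-calorie residual procedure. Only the heading of that appendix is legible in the text available here.

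**The concern.** Read literally, the residual rule cannot be carried out at the rate where every full-calorie patient begins: the instruction to restart gives no feed. It also treats one finding in two ways. A GRV above 400 cc discovered after regurgitation leads to a hold and a restart with a minimum. A GRV above 400 cc that persists at routine checks leads to a hold and a restart without one. The protocol gives no reason for the difference.

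What is at stake is uniform delivery of the intervention. Feeding volumes are not blinded, and section 5.1.7 aims to standardize the response to intolerance. Where the written rule gives zero or a negative rate, each site has to improvise. While a full-calorie patient sits at 0 cc/hr, that patient also receives less than a trophic patient restarted after the same event, which reverses the intended contrast for that interval.

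**Working it through.** The plan gives no figure of its own to reproduce on this point. The check is direct arithmetic on the written rules.

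**Inputs.** Starting rate 25 cc/hr and step 25 cc/hr every 6 hours (5.1.3.2); reduction 25 cc/hr with no stated minimum, residual checks every 6 to 12 hours and a 2-hour recheck (5.1.4.2); reduction 25 cc/hr with minimum 10 cc/hr (5.1.7.1 to 5.1.7.4); trophic restart 20 kcal/hr (5.1.4.1).

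**Step 1: the two forms.** Let r be the rate before the hold, in cc/hr.

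- Section 5.1.4.2: restart = r - 25.
- Sections 5.1.7.1 to 5.1.7.4: rate = the larger of 10 and r - 25.

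| Previous rate r | 5.1.4.2 as written | Form with the 10 cc/hr minimum |
|---|---|---|
| 10 | -15 | 10 |
| 25 | 0 | 10 |
| 30 | 5 | 10 |
| 35 | 10 | 10 |
| 50 | 25 | 25 |
| 75 | 50 | 50 |

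The forms agree when r - 25 is at least 10, that is, from r = 35 upward. They differ only below 35 cc/hr.

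**Step 2: can the case arise?** Yes. A first high residual at 6 hours, before any advance, keeps the rate at 25 cc/hr. A second high residual 2 hours later triggers the hold with a previous rate of 25 cc/hr. A rate of 10 cc/hr can also arise: a patient at 25 cc/hr who has distention or vomiting goes to the larger of 10 and 0, which is 10. A residual hold from there gives 10 - 25 = -15 cc/hr.

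**Step 3: size of one episode.** Assume that the restart at 0 cc/hr lasts until the next residual check, 6 to 12 hours later, and that the residual is then acceptable so that feeds advance. Against the trophic restart:

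- 6 h x 20 kcal/hr = 120 kcal
- 12 h x 20 kcal/hr = 240 kcal

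Against the form with the 10 cc/hr minimum, at a previous rate of 25 cc/hr, the difference is 10 cc/hr x 6 to 12 h = 60 to 120 cc of formula.

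**The case against.** The strongest objection is that the operative rule may sit in Appendix D. Section 5.1.4 directs rate adjustment for high residuals to that appendix, and its chart is not legible here. Section 5.1.4.2 is silent on a minimum; it does not rule one out. This stands as a limit on the finding. A reader might infer that the protocol has no minimum at all for residual holds, but the available text cannot show that. It shows a gap in 5.1.4.2 when set beside 5.1.7.1 to 5.1.7.4. If the chart does state a minimum, the section text still omits it and needs aligning.

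The second objection is that this is a rare edge case. It needs two residuals above 400 cc at a low rate, and six hours at 25 cc/hr delivers only 6 x 25 = 150 cc. The phase II interim data in section 1.4 show a mean of 11 hours to goal rate, only 4% never reaching it, and 950 against 220 cc per day delivered. The monitoring board also reviews group separation by delivered volume. This stands too. A reader might infer that the rule leaves the full-calorie arm unfed or erodes the caloric contrast under test, but the documents give no frequency and do not support that.

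A reader might also charge the episode at the full trophic daily amount, 20 x 24 = 480 kcal. That overstates it, because 5.1.4.2 allows feeds to advance at the next acceptable check. Nor does any rule return patients to 25 cc/hr as such: the reductions run from the previous rate, so 25 cc/hr results only from 50 cc/hr. Finally, whether 10 cc/hr is itself a suitable minimum beside the trophic rate is a clinical question. The four 5.1.7 rules apply that value consistently, so it is no evidence of a contradiction.

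What the objections do not remove is that the written instruction yields zero at the starting rate and a negative number at 10 cc/hr, and that it differs without explanation from the regurgitation rule for the same residual threshold.

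**Conclusion.** The point holds as a local inconsistency. Section 5.1.4.2, as written, cannot be carried out as a restart at previous rates of 25 cc/hr or less, and it departs from the four companion rules at any previous rate below 35 cc/hr. It reaches full-calorie patients from the first hours, and trophic patients once they advance after 144 hours.

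The consequence is small: about 120 to 240 kcal per episode against the trophic restart. That figure rests on a restart at 0 cc/hr and an advance at the next 6 to 12 hour check. No effect on ventilator-free days, on the analysis or on trial-wide separation is shown. The conclusion concerns the section text only, since Appendix D could not be read. The reason to act is that a standardized rule should give every site the same instruction it can follow, and the correction costs almost nothing.

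**What to change.** Reconcile 5.1.4.2 with 5.1.7.1 to 5.1.7.4 and with the Appendix D chart, so that one restart rule that can be carried out governs residual holds in the full-calorie arm and in trophic patients after 144 hours. The text should say whether a minimum applies. If residual holds are meant to differ from the other intolerances, say so and state what is done when the subtraction gives zero or less. Which value applies is the sponsor's clinical decision.

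The cost is one phrase in 5.1.4.2 and a check of the Appendix D chart. The sample size, endpoints and analysis are not affected.
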